# Objective 2: To evaluate the long-term effectiveness and safety of Vimizim.

The long-term effectiveness of Vimizim will be evaluated as described below using clinical outcome variables as specified in Table 8.1.1.1 based on measurements at baseline through discontinuation or end of follow-up (which ever occurs first) based on the ERT-treated patients in the Full Analysis Set population. The measurement closest to the index date during the baseline period will be used to describe patients prior to initiating therapy (i.e. 'baseline measurement'), with the exception of uKS. For uKS, the 'baseline measurement' will be restricted to measurements occurring during the baseline period prior to or at index. As MPS IVA is a degenerative disease (Harmatz , 2013), a sensitivity analysis will be conducted for the outcomes of 6MWT, respiratory function, height, weight, and uKS limiting the baseline period to the 6 months before index and 30 days after index (with the same caveat for uKS as the primary analysis).

Whenever possible and/or relevant to the outcome, outcomes will be described graphically accounting for time and/or age at the assessment. When warranted by the outcome of interest, outcomes will be summarised as event rates censored at time of discontinuation or data cutoff. Change and/or percent change from baseline to follow-up outcome measurements after pre-specified amounts of exposure (e.g. after 1 or 5 years of exposure) will only be summarised for patients with a baseline measurement and a relevant follow-up measurement (near the specified time) prior to discontinuation. Additional details of analyses can be found in the SAP.

Long-term safety events occurring during MARS after index or registry entry (which ever occurs later), including hypersensitivity events, will be evaluated by summarising the incidences of AEs by System Organ Class, Preferred Term, relationship to Vimizim, and severity in the Safety Population. Exposure-adjusted incidence rates and event rates while on treatment will be included as part of long-term safety evaluation. All AE summaries will include only treatment-emergent adverse events (TEAEs) and SAEs reported during the study period (AEs that occur after the first Vimizim infusion). Analyses of AEs of hypersensitivity and anaphylaxis, and AEs temporally related to a Vimizim infusion will be summarised by System Organ Class, PT, and severity All AEs will be coded using the most recent version of Medical Dictionary for Regulatory Activities (MedDRA).

Total and neutralizing antibody status will be summarised over the follow-up period.

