# 11.1 Timepoints

Among enzyme replacement therapy (ERT)-treated patients:

- Registry Entry is defined as at the date of patient signed consent to participate in MARS
- Index is defined as the date of first exposure to Vimizim (may precede or follow Registry Entry)
- Baseline is defined as within 12 months prior to index or within 1 month after index. Historic data prior to index collected with the data point closest to index in the 12 months prior to index or 1 month after index (except for measurement of urinary keratan sulfate [uKS]) is considered the baseline measurement
- Follow-up is defined as the time period after index plus 1 month (Index Date + 30 days +1) to last data point.

Among ERT-naive patients:

- Registry Entry is defined as at the date of patient signed consent to participate in MARS
- Follow-up is defined as the time period from Registry Entry (exclusive) to last data point

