# Objective 1: To characterize and describe the MPS IVA population as a whole, including the heterogeneity, progression, and natural history of MPS IVA.

In order to characterise and describe the MPS IVA population as a whole, clinical outcomes variables as specified in Table 8.1.1.1 and demographics will be summarised in the 12 months prior to or 90 days after Registry Entry (for consistency with data entry at Registry Entry) stratified by ERT status at Registry Entry. The measurement closest to Registry Entry during this period will be used to describe patients. The natural history and progression of MPS IVA will be described in ERT-naïve and ERT-treated patients based on measurements while not on ERT treatment (i.e. all measurements for ERT-naïve and prior to index for ERT-treated), with progression of the disease based on measurements of clinical outcomes described over time and presented by age.

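### For every Objective 2 outcome except uKS, a value taken up to 1 month after the first Vimizim dose can serve as the pre-therapy baseline, and the planned sensitivity analysis cannot show the effect

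*Protocol*

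**What the plan says.** **Objective 2.** Protocol Section 11.1 sets the window: "Baseline is defined as within 12 months prior to index or within 1 month after index". Index is the date of first Vimizim exposure. Section 18.1.7 then states how one value is chosen: "The measurement closest to the index date during the baseline period will be used to describe patients prior to initiating therapy". Closeness is counted on either side of index, with no preference for the earlier side. The chosen value is the reference for "Change and/or percent change from baseline to follow-up outcome measurements after pre-specified amounts of exposure".

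One outcome is treated differently: "For uKS, the 'baseline measurement' will be restricted to measurements occurring during the baseline period prior to or at index".

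The sensitivity analysis covers 6MWT, respiratory function, height, weight and uKS, and works by "limiting the baseline period to the 6 months before index and 30 days after index". uKS keeps its restriction there. The reason given is that the disease is degenerative.

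**Objective 1.** Clinical outcomes and demographics are "summarised in the 12 months prior to or 90 days after Registry Entry", stratified by ERT status at Registry Entry, using the value closest to entry. The natural-history and progression analysis that follows uses only measurements made off ERT, which for ERT-treated patients means before index.

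**Related definitions.** Section 18.1.5.3 defines time on ERT as infusion date plus 7 days. Section 11.1 starts follow-up at index plus 31 days.

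**The concern.** A value is labelled as describing the patient before therapy when the patient may already have been dosed. A 6MWT on day 5 after index displaces one on day 10 before it. Yet Section 18.1.5.3 counts day 5 as time on treatment, and the natural-history part of Objective 1 would exclude that same visit.

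Effectiveness under Objective 2 is measured as change within treated patients, so the baseline is the reference for every such result. The same approach is carried into Objective 5 (index before age 5 years) and, if a treatment passes the 5% use threshold, into Objective 4. Any gain made before the baseline was taken is subtracted from the reported change.

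Under Objective 1 the exposure is narrower. A patient not on ERT at Registry Entry who starts Vimizim on day 10 and has the closest measurement on day 60 is described in the not-on-ERT stratum with an on-treatment value.

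**Working it through.** The protocol gives no figure for this point, so there is none to reproduce. The check asks how often a post-index value would be chosen and how much that could matter.

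**Inputs from the protocol.** Window of 12 months before to 1 month (30 days) after index; sensitivity window of 6 months (183 days) before to 30 days after; closest value chosen; infusion interval of 7 days, inferred from the 7-day rule in Section 18.1.5.3; 24 weeks (168 days) as the MOR-004 treatment period in Table 6.1.1.

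**Assumptions.** Visits evenly spaced every G days at random phase to index; effect accruing linearly over 168 days. The protocol supports neither, and visit frequency is left to local care.

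**1. Infusions inside the windows.** Days 0, 7, 14, 21 and 28 give 5 by day 30. Under Objective 1, days 0 to 84 give 13 by day 90 if Vimizim starts on the day of entry.

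**2. Share of baselines taken after index.** If the next visit falls u days after index, the previous one lies G − u days before it. The later value is chosen when u ≤ 30 and u < G − u. For G above 60 days the share is 30/G. For monthly visits it is one half.

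In the 6-month sensitivity window with annual visits, a baseline exists only if u ≤ 30 or 365 − u ≤ 183. That is 30 + 183 = 213 of 365 phases, so the share is 30/213. Simulating the rule gave the same shares.

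| Visit spacing | Primary window | Sensitivity window |
|---|---|---|
| Annual (365 days) | 30/365 = 8% | 30/213 = 14% |
| 6-monthly (183 days) | 30/183 = 16% | 16% |
| 3-monthly (91 days) | 30/91 = 33% | 33% |
| Monthly (30 days) | 50% | 50% |

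The sensitivity window never lowers the share, and with annual visits it raises it.

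**3. Average attenuation under linear accrual.** For visits 3 or more months apart, a post-index baseline falls on average at day 15, when 15/168 = 8.9% of the 24-week effect is present. Attenuation = share × fraction reached:
- annual: 0.082 × 0.089 = 0.7%
- 6-monthly: 0.164 × 0.089 = 1.5%
- 3-monthly: 0.330 × 0.089 = 2.9%

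**4. Range if the effect comes faster.** If 10% to 50% of the effect is already present at the post-index value, attenuation is about 1-4% at a share of 8%, 2-8% at 16% and 3-17% at 33%.

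**The case against.** Several counter-arguments have weight.

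- **The sensitivity analysis has another purpose.** It tests for stale pre-index values in a degenerative disease, and shortening that side suits the purpose. This stands. The point is only that no planned analysis isolates post-index values.
- **uKS may differ for good reason.** Section 11.23.3 treats a rise in uKS as a sign of changed pharmacodynamic activity, so a stricter rule for a biomarker than for function or growth is a defensible choice. A reader might infer that the exception proves the sponsor saw the problem for the other outcomes. The protocol does not say so, nor does it say that those outcomes respond within 30 days.
- **An older value is not always better.** A height or 6MWT from 12 months before index can be a worse baseline than one from the day after, especially in growing children. This stands and limits the fix.
- **The analyses are descriptive.** There are no hypotheses, p-values are nominal, and days 1-30 are outside follow-up, so no value counts as both baseline and follow-up. This lowers the stakes but does not make the pre-therapy label correct.

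A reader might also take the 90-day window as a second baseline standing for untreated status, with the sensitivity analysis repeating its fault. The protocol does not support that. The window is anchored on Registry Entry, describes treated and untreated patients alike, and lies outside the sensitivity analysis, which belongs to Objective 2.

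**Conclusion.** The point holds for Objective 2 outcomes other than uKS: an on-treatment value can be used, and can displace a nearby pre-index value, as the measurement said to precede therapy. The planned sensitivity analysis cannot show the consequence. The direction, if Vimizim acts within the first month, is toward no change.

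The average size is probably small: about 1-3% of the 24-week effect under linear accrual and 3- to 12-monthly visits, and more if the effect comes early and visits are frequent. The protocol does not allow a firm estimate. It would be tempting to quote 30/168 = 18% and 90/168 = 54% as the bias. Those describe a single patient measured on the last day of each window (for the second, one who also started Vimizim on the day of entry), under the same linear assumption. MOR-004's stated objective concerns 6MWT, so carrying its time scale to height, weight or spirometry is a further step that the protocol does not support.

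Under Objective 1 only the description of patients not on ERT at entry is exposed, and only for those who start Vimizim within 90 days. The natural-history analysis is unaffected.

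**What to change.** 1. **Add a sensitivity analysis** for 6MWT, respiratory function, height and weight that uses only values on or before index, as is already done for uKS. Keeping the 12-month window would change one thing at a time.
2. **Primary analysis:** where a pre-index value exists within the 6 months before index, a window the protocol already uses, take it in preference to a post-index value. Otherwise keep the closest-value rule. Report how many baselines are post-index, by outcome.
3. **Objective 1:** for patients not on ERT at Registry Entry, end the 90-day window at index.

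Under the even-spacing assumption, step 2 takes the post-index share to zero for 3- and 6-monthly visits, because a value within 183 days before index then always exists. With annual visits the 8% remains: when the next visit falls within 30 days after index, the last one was at least 335 days before it. Step 1 covers that case.

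No new data are needed. The cost is wording in the protocol and SAP; Section 18.1.8 lets the SAP prevail where the two differ. Some primary baselines become somewhat older, and patients whose only value in the window falls on days 1-30 drop out of the added sensitivity analysis. The protocol gives no data to size that loss.

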#### 10.1 Withdrawal of Patient from the Registry

Patients (or their legally authorised representatives) may withdraw their consent to participate in the Registry at any time without prejudice. The Investigator must withdraw from the Registry any patient who requests to be withdrawn. A patient's participation in the Registry may be discontinued at any time at the discretion of the Investigator and in accordance with his/her clinical judgment.

BioMarin also reserves the right to discontinue the Registry at any time for either clinical or administrative reasons (with concurrence of Regulatory Agencies) and to discontinue participation by an individual Investigator or site for poor enrolment or noncompliance.

Reasons for which the Investigator or BioMarin may withdraw a patient from the Registry include, but are not limited to, the following:

- Patient was erroneously admitted into the Registry or does not meet entry criteria
- Patient was lost to follow-up

Specific reason for withdrawal of consent from the Registry will be captured in the Registry database. The Investigator or designee must explain to each patient, before enrolment into the Registry, that, for evaluation of Registry results, the patient's protected health information obtained during the Registry may be shared with the Registry sponsor, regulatory agencies, and IRB/IEC/REB. It is the Investigator's (or designee's) responsibility to obtain written permission to use protected health information per country-specific regulations, such as the Health Insurance Portability and Accountability Act in the US, from each patient or, if appropriate, the patient's legally authorised representative. If permission to use protected health information is withdrawn, it is the Investigator's responsibility to obtain a written request and to ensure that no further data will be collected from the patient and the patient will be removed from the Registry.

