# 18.1.5.3 Treatment Groups

ERT-naïve patients are defined as the group of patients who had never received Vimizim either prior to the Registry enrolment, or during Registry participation. ERT-treated patients are defined as the group of patients who had received at least 1 dose of Vimizim either prior to the Registry enrolment, or during Registry participation. Time on ERT treatment (defined as ERT infusion date +7 days) and not on treatment during follow-up will be identified.

Analysis of clinical outcomes, demographic and baseline characteristics will be conducted, stratified by the 2 treatment groups (ERT-naïve patients vs ERT-treated patients). Due to the observational nature of the Registry, ERT-treated patients may discontinue treatment. Treatment discontinuation will be defined based on the stop date reported in the enzyme replacement log plus 7 days (to include events potentially occurring 'on treatment' before the next anticipated infusion, if the date of last infusion was the documented stop date). Outcome analyses among the ERT-treated will generally be censored at the time of discontinuation (i.e. an 'as treated' analysis). Exceptions to this convention will be detailed in the SAP.

If there are significant numbers of patients who discontinue treatment and re-initiate, sensitivity analysis may be performed by describing outcomes during the period of re-initiation.

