# 18.1.6 Handling of Dropouts and Missing Data

Patients who discontinued the Registry prematurely will not be replaced. The following missing data imputation rules will apply to all analyses unless otherwise specified elsewhere in the SAP. Missing dates or partially missing dates will be imputed conservatively for concomitant medications and AEs to ensure that an AE is considered treatment emergent and has the longest possible duration. Data in regards to reason for drop out or discontinuation of the Registry will be analysed.

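### Objective 2 gives two different ends of observation; the one for event rates, read literally, understates effectiveness rates when treated patients leave or die without a logged stop date

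*Protocol*

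**What the plan says.** Four places in the Protocol bear on when observation of an ERT-treated patient ends.

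- Section 18.1.7, Objective 2, first paragraph: effectiveness is evaluated "based on measurements at baseline through discontinuation or end of follow-up (which ever occurs first".
- Section 11.1, for ERT-treated patients: "Follow-up is defined as the time period after index plus 1 month (Index Date + 30 days +1) to last data point".
- Section 18.1.7, Objective 2, second paragraph, for outcomes where a rate is warranted: "outcomes will be summarised as event rates censored at time of discontinuation or data cutoff".
- Section 18.1.5.3: "Treatment discontinuation will be defined based on the stop date reported in the enzyme replacement log plus 7 days". The same section adds: "Outcome analyses among the ERT-treated will generally be censored at the time of discontinuation (i.e. an 'as treated' analysis", and then "Exceptions to this convention will be detailed in the SAP".

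Leaving the Registry is foreseen separately. Section 10.1 lists "Patient was lost to follow-up" among the reasons for withdrawing a patient, and Section 18.1.6 states "Patients who discontinued the Registry prematurely will not be replaced". No section names loss to follow-up, withdrawal from the Registry or death as a censoring time for event rates.

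**The concern.** The last data point belongs to the patient. Data cutoff is an administrative date common to everyone. The two roughly coincide only for patients observed up to the cutoff. Discontinuation does not close the gap, because it means stopping Vimizim as recorded in the ERT log. A patient lost to follow-up may still be receiving Vimizim elsewhere, so the site may have no stop date to enter.

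Under the event-rate wording, such a patient adds person-time from exit to cutoff, and no event can be recorded in that time. The numerator stops while the denominator continues. The outcomes listed in Section 18.1.7 that lend themselves to rates, such as surgeries and respiratory infections, are unfavourable ones, so a rate that is too low flatters Vimizim. Objectives 4, 5 and 7 repeat or follow the Objective 2 analyses and would inherit the error.

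**Working it through.** The protocol states no event rate, attrition rate or target sample size for this point (Section 18.1.2 says that size is not set by power), so there is no figure to reproduce. The direction follows from the wording; the size can only be illustrated.

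**Inputs**
- Horizon T = 10 years: data collection runs from Q3-2014 to September 2024 (Section 5).
- Minimum of 2 years of collection after the last enrolment (Section 10), used for the staggered-entry case.
- Annual loss a without a logged stop date: assumed at 1%, 2%, 5% and 10%.
- Constant exit hazard d = −ln(1 − a). The event rate is constant and unrelated to exit. Events are seen only until exit.

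**Formula.** Mean person-time observed per patient is (1 − e^(−dT))/d. Person-time counted under the literal rule is T. The reported rate divided by the correct rate is therefore [(1 − e^(−dT))/d]/T.

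For a = 5%: d = 0.05129 and e^(−10d) = 0.95^10 = 0.5987. Observed person-time is (1 − 0.5987)/0.05129 = 7.82 years against 10 counted, a ratio of 0.782.

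| Annual loss (assumed) | T = 10 years | Uniform entry, 2 to 10 years |
|---|---|---|
| 0% | 1.000 | 1.000 |
| 1% | 0.951 | 0.966 |
| 2% | 0.905 | 0.934 |
| 5% | 0.782 | 0.844 |
| 10% | 0.618 | 0.716 |

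The last column divides the average observed person-time over T = 2 to 10 by the average T.

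**If some exits have a stop date.** Let f be the share of exits without one. Counted person-time becomes 7.82 + f × (10 − 7.82). At 5% loss and T = 10:
- f = 0: ratio 1.000
- f = 0.25: 7.82/8.37 = 0.935
- f = 0.5: 7.82/8.91 = 0.878
- f = 1: 0.782

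**Example with round, assumed numbers.** Take 100 patients and 10 years, with 30 lost at year 4 and no stop date, and a true rate of 0.10 per year. Observed person-time is 70 × 10 + 30 × 4 = 820 years, giving 82 expected events. The correct rate is 82/820 = 0.100. The literal rule gives 82/1,000 = 0.082.

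**Sensitivity to recorded discontinuation.** Adding a logged treatment discontinuation of 5% a year changes little: at T = 10 the ratios become 0.955, 0.913, 0.799 and 0.646 for the four loss rates.

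**The case against.** The best defence is that the first paragraph of Objective 2 governs what follows it. On that reading the event rates already sit inside the limit of discontinuation or end of follow-up, and data cutoff is only the administrative end for patients still under observation. The SAP, which is not at hand, is promised for further detail, and Section 18.1.8 lets it prevail. This is a fair reading, and the protocol nowhere says that patients who have left stay at risk. But the first paragraph limits which measurements count; the only sentence that sets censoring for event rates uses the other end point. The protocol is therefore not silent and leaving detail to the SAP. It fixes a rule, and that rule conflicts with its own definition of follow-up. Section 18.1.5.3 defers only exceptions to the discontinuation convention.

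Safeguards also reduce the number of missing stop dates. ERT duration should be recorded (Section 11.11), blank eCRF fields are generally not accepted (Section 16.2), sites are visited about twice a year with calls in between (Section 19.1), and death in a treated patient is a reportable SAE (Section 22.1). These make missing stop dates less common but do not exclude them.

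A reader might infer more than the documents support:
- *That every event rate is too low.* The sentence covers Objective 2 effectiveness outcomes summarised as rates, and analyses that repeat them. Adverse-event rates have their own on-treatment, exposure-adjusted wording, although a missing stop date could affect that exposure time as well. Change-from-baseline summaries are not rates.
- *That patients who die are treated as event-free.* Events before death are counted. Only time after death is at issue, and only without a stop date.
- *That any withdrawal of consent ends data collection under Section 10.1.* That consequence is tied to withdrawal of permission to use health information, and such a patient is removed from the Registry.
- *That death must be handled as a competing event in the protocol.* That choice can be left to the SAP.

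**Conclusion.** The point holds as an inconsistency between two stated end points, one of which gives a wrong denominator if followed as written. The direction is certain for any affected rate: person-time in which no event can be recorded can only lower it. The size is not established. It ranges from no bias, when every exit has a stop date or nobody is lost, to a reported rate of 0.618 of the correct one at an assumed 10% annual loss over 10 years with no stop dates. A middle case of 5% annual loss with half the exits logged gives 0.878. All figures rest on assumed attrition, a constant exit hazard and an event rate unrelated to exit. The documents do not show that any rate has been or will be understated by a given amount.

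**What to change.** In the second paragraph of Objective 2, replace the censoring phrase with: *censored at the earliest of treatment discontinuation (stop date + 7 days), death, withdrawal from the Registry, end of follow-up (last data point) and data cutoff*. State that the same end point closes the person-time denominator, and apply it wherever Objective 2 is repeated (Objectives 4, 5 and 7). The SAP should use the same wording.

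The cost is a sentence or two and no new data collection for the main element, since every patient with data has a last data point. The protocol does not expressly say that a last-contact date is collected, so the rule should not depend on one. The downside is slightly less person-time, including the gap between the last visit and the cutoff for patients still enrolled, and somewhat less favourable rates.

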No specific criteria have been established for the conclusion or early termination of the Registry; however, the approval of new treatments that alter the course of the disease may impact the direction of the program. Investigators will determine the actual frequency of necessary assessments according to a patient's individualized need for medical care and routine follow-up. Data may be collected for all or some of the assessments as outlined in Table 8.1.1.1 dependent upon the patient's current SOC. The Registry will enroll and collect data on patients according to current SOC over a period of at least 8 years from the time of the first marketing approval globally, and data on individual patients will

Page 29

continue to be collected for at least 2 years from the time that the last patient was enrolled or until the Registry is completed. All of the Registry-specific clinical data collected will be entered into the Registry database.

Page 30

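### Change after 1 or 5 years of exposure is subtracted from a baseline up to 12 months older than the first dose, so a 1-year change can span 11 to 24 months and include untreated time

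*Protocol*

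**What the plan says.** Protocol Section 11.1 sets time zero: "Index is defined as the date of first exposure to Vimizim (may precede or follow Registry Entry". It then sets the baseline window: "Baseline is defined as within 12 months prior to index or within 1 month after index".

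Section 18.1.7, Objective 2, chooses the value within that window: "The measurement closest to the index date during the baseline period will be used to describe patients prior to initiating therapy". There is one exception: "For uKS, the 'baseline measurement' will be restricted to measurements occurring during the baseline period prior to or at index". The effectiveness summary is "Change and/or percent change from baseline to follow-up outcome measurements after pre-specified amounts of exposure (e.g. after 1 or 5 years of exposure", restricted to patients who have both a baseline value and a follow-up value near the nominal time and before discontinuation. The width of the follow-up window is not given.

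The same section notes that the disease is degenerative and plans a sensitivity analysis "limiting the baseline period to the 6 months before index and 30 days after index", for the "outcomes of 6MWT, respiratory function, height, weight, and uKS". It also promises graphs that take account of time or age where possible. Section 18.1.4 makes a similar commitment for summaries over time.

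Visits are not fixed by the Registry. Section 8.1 states: "Investigators will determine the actual frequency of necessary assessments according to a patient's individualized need for medical care and routine follow-up".

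**The concern.** The label on the change and the subtraction behind it use different starting points. The label counts time from the first dose. The subtraction starts at the date of the baseline measurement, which can be up to a year earlier. Whatever happened in the gap is tabulated as change on treatment.

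The direction differs by outcome. Growth before treatment is added to the height gain on drug, which matters most under Objective 5, where the Objective 2 analyses are repeated for children who started before age 5. Decline before treatment in walking distance or lung function counts against the drug. The size differs between patients according to when each was last measured.

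The protocol treats the same period differently elsewhere. Objective 1 counts measurements before the first dose in treated patients as natural history. Section 18.1.5.3 ends the as-treated period 7 days after the recorded stop date. So the end of the interval is limited to days, while its start may hold 12 untreated months.

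**Working it through.** The protocol states no baseline-to-follow-up interval, so there is no figure to reproduce. The check is date arithmetic.

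**Inputs**
- Primary baseline window: 12 months before to 1 month after index; for uKS, 12 months before to index (Section 11.1; Section 18.1.7, Objective 2).
- Sensitivity window: 6 months before to 30 days after index, taken here as 1 month; for uKS, 6 months before to index (Objective 2).
- Follow-up time T: 12 or 60 months after index (Objective 2).
- Schedule in Table 8.1.1.1: six-monthly for 6MWT, 3MSCT, respiratory function, anthropometrics and uKS; annual for EQ-5D-5L.

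**Extremes, with follow-up at exactly T**

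Shortest interval = T − post-index allowance. Longest = T + pre-index allowance. Largest untreated share = pre-index allowance / longest interval.

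| Window | T = 12 | Untreated, at most | T = 60 | Untreated, at most |
|---|---|---|---|---|
| Primary | 11 to 24 | 12/24 = 50% | 59 to 72 | 12/72 = 17% |
| Primary, uKS | 12 to 24 | 50% | 60 to 72 | 17% |
| Sensitivity | 11 to 18 | 6/18 = 33% | 59 to 66 | 6/66 = 9% |
| Sensitivity, uKS | 12 to 18 | 33% | 60 to 66 | 9% |

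Under the primary rule two patients' 1-year intervals can differ by a factor of 24/11 = 2.2. If an outcome moves at a constant rate and the drug does nothing, the reported 1-year change lies between 11/12 = 0.92 and 24/12 = 2.0 times the annual change.

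**Typical size**

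Assume regular visits at random phase to index. Mean interval = T − mean baseline time.

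- *Six-monthly visits.* The last value before index is 0 to 6 months old. If it is more than 5 months old, the next visit falls within 1 month after index and is closer, so it is chosen. Baseline times are then uniform from −5 to +1, with mean −2. Mean intervals are 12 + 2 = 14 months (14/12 = 1.17) and 60 + 2 = 62 months (62/60 = 1.03).
- *uKS, six-monthly.* No value after index is allowed, so baseline times are uniform from −6 to 0, with mean −3. Mean intervals are 15 months (15/12 = 1.25) and 63 months (63/60 = 1.05).
- *Annual assessments.* By the same reasoning baseline times are uniform from −11 to +1, with mean −5. Mean intervals are 17 months (17/12 = 1.42) and 65 months (65/60 = 1.08).

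The means need follow-up to be at T only on average. The extremes need it at exactly T. If the unstated follow-up window were ±1, ±3 or ±6 months, the 1-year range would widen to 10–25, 8–27 or 5–30 months.

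**The case against.** The protocol has seen the problem. It names degeneration as its reason for the narrower baseline window, and that analysis covers five main outcomes. Baseline is the value closest to index, so a patient measured shortly before the first dose has an interval close to nominal. On a true six-monthly schedule nearly every baseline already falls inside the narrower window. The summaries are descriptive, p-values are nominal, 1 and 5 years are given only as examples, and the objective is long-term, where the error is small. Follow-up windows and interval reporting are ordinary SAP content, and Section 18.1.8 lets the SAP prevail.

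Much of this stands, and it rules out stronger readings. A reader might infer that measurement dates are ignored altogether. They are not: baseline is selected by date, and graphs and summaries by time or age are promised. A reader might also spread baselines evenly over the whole window and conclude that the mean 1-year interval is 17.5 months, 46% too long. No document supports that spread, and the closest-value rule works against it. Nor does the rule make every patient's on-drug change wrong.

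Three things do not fall to the objection. The baseline rule and the exposure label are fixed in the protocol itself. The narrower window still allows 18 months at 1 year and omits 3MSCT, EQ-5D-5L and other change outcomes. And the schedule is only a guide: care is individual, Section 20 concedes that assessments may be missing, and a first dose may precede Registry entry, so baselines may come from older records.

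**Conclusion.** The point holds for the numerical change-from-baseline tables. As the rule stands, a change labelled 1 year can cover 11 to 24 months (uKS 12 to 24), of which up to 12 may be untreated. At 5 years the range is 59 to 72 months (uKS 60 to 72).

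The likely average error is smaller: 17% at 1 year and 3% at 5 years for six-monthly outcomes, 25% and 5% for uKS, and 42% and 8% for annual ones. These averages rest on regular visits at random phase to the first dose and follow-up centred on the nominal time. Sparser standard-of-care visits would lengthen the gaps. Visits arranged around the start of treatment would shorten them.

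This is worth correcting for the 1-year figures and is minor at 5 years. The SAP is not shown and may already scale or report the intervals; the protocol does not.

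**What to change.** Keep the 12-month window so that no patients are lost from the main summary. Then, for the numerical change tables:

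1. Beside each raw change, report the median and range of the baseline-to-index and baseline-to-follow-up intervals, and the change per elapsed year from actual dates. State that annualising corrects the interval length but not the untreated share.
2. Extend the 6-month-window sensitivity analysis to every outcome summarised as change from baseline, including 3MSCT and EQ-5D-5L.
3. Optionally, where enough patients have repeated values before the first dose, add a supportive model in actual time from index for key outcomes. It should not replace the tables: early values may be sparse, and growth is not linear through childhood.

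The cost is a little more analysis and table space. The dates are already needed to apply the window. The narrower-window analysis will hold fewer patients for annual outcomes. With baselines uniform from −11 to +1, those older than 6 months are 5/12 = 42%, which is why it should stay a sensitivity analysis.
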